5.0 STUDY PROCEDURES

Table 5: Study timeline

	Screening ^{a,b,c}	Induction (7 days) ^c	Cycle 1 (Cycle=28 days)			Cycle 2-4		Cycle 5 +	End of Treatment ^o	Follow Up ^p
		D1	D1	D8	D15	D1	D15	D1		
Study window				±1 day	±1 day	±3 days	±3 days	±3 days	±7 days	q3months
Informed Consent	X									
Medical History	X		X	X		X		X	X	
Physical Exam	X	X	X	X	X	X	X	X	X	
Vitals signs ^{d,i}	X	X	X	X	X	X	X	X	X	
ECOG PS	X	X	X	X			X	X	X	
AE reporting ^q		X	X	X	X	X	X	X	X ^q	X ^q
Concomitant Medications		X	X	X	X	X	X			X
CMP ^e	X	X	X	X	X	X	X	X	X	
CBC with differential ^f	X	X	X	X	X	X	X	X	X	
Pregnancy test ^g	X ^g		X							
Thyroid function test ^h	X									
PT/INR	X ⁱ									
Imaging (CT or MRI) ^j	X					X ⁱ		X ^j	X	
Tumor biopsy ^k	X									
Mutation testing	X ^r									
Blood for Tumor Markers ^l		X	X			X ^l			X	
Nivolumab infusion ^m			X		X	X	X	X ^m		
Veliparib ⁿ		X	X			X		X		
Survival										X

- Informed consent must be signed ≤ 30 days before registration. If signature is outside that window the patient must sign a new consent.
- Pre-study H&P and all labs must be ≤ 14 days before registration. Tumor measurements and radiologic evaluations must be ≤28 days before registration.
- The maximum time interval between registration and the first dose of study drug will be 14 days.
- Vital signs include pulse and blood pressure. Weight will be recorded at baseline. Height will be recorded at baseline only.
- Serum Chemistry will include calcium, chloride, magnesium, phosphorus, creatinine, sodium, potassium, blood urea nitrogen, bicarbonate, glucose, total bilirubin, aspartate aminotransferase (AST), alanine aminotransferase (ALT), alkaline phosphatase, albumin, and total protein.

- f. CBC: Performed pre-dose at each treatment visit (Day 1 & 15 of Cycles 1-4, and Day 1 of Cycle 5+). For patients experiencing significant drop in WBCs or platelets felt related to treatment, CBCs should be obtained more frequently (weekly or more frequently) to assess timing for retreatment or need for transfusion support.
- g. Serum or urine test only for women of childbearing potential; must be tested within 7 days prior to registration as well as C1D1 (within 24 hours prior to nivolumab treatment).
- h. Thyroid function tests will include thyroid stimulating hormone (TSH) with reflexfree T4. This will be done at baseline then only as clinically indicated thereafter.
- i. PT/INR is required at baseline (≤ 28 days prior to registration) for patients on anticoagulants.
- j. Imaging (either CT scan or MRI and PET if applicable) will be performed at screening, ≤ 28 days prior to registration. The same modality used at baseline should be used throughout for imaging. CT imaging will include chest, abdomen, and pelvis. Neck will be included only if measurable lesions are present. Scans will then take place every 2 cycles (8 weeks) starting with Cycle 3 Day 1 (- 7 days). Tumor measurements will be performed using RECIST 1.1 or Lugano classification. Progressive Disease (PD) must be confirmed by repeat scan within 8 weeks.
- k. Patients will undergo a fresh tissue biopsy prior to study enrollment, unless deemed to be clinically inappropriate per PI. If a fresh biopsy is not feasible, an archival tissue sample should be obtained (a cell block is preferred, however 15 unstained slides will suffice). Tissue should be obtained by any means possible, but patients will not be excluded from the study if tissue is not available. The samples will be obtained for correlative studies – see section 9.0 and separate lab manual for details.
- l. Study labs will be collected for tumor markers pre-dose on Induction Day 1, C1D1, C3D1, and at the End of Treatment visit. See section 9.0 and separate lab manual for more details.
- m. Nivolumab will be administered as follows:
 - Cycles 1-4: given at a fixed dose of 240mg IV over 30 minutes (-5 / +15 minutes) every 2 weeks
 - Starting with Cycle 5 Day 1: 480mg IV over 30 minutes (-10 / +15 minutes) every 4 weeks until disease progression, intolerability, or withdrawal of consent.
 - Vital signs will be monitored prior to, throughout, and after the nivolumab infusion according to Table 4.2.
- n. Veliparib will be taken orally at the assigned dose twice a day until disease progression, intolerability, or withdrawal of consent. It will be initiated as monotherapy during a 7-day induction period. Starting with Cycle 1 Day 1, veliparib will be given twice daily in combination with scheduled nivolumab infusions. Veliparib may be taken with or without food. Patients will be given a drug diary to maintain for compliance. Veliparib dosing may take place independently of nivolumab. On the day of a study visit, lab values should be checked against sections 4.4 and 4.5 for continued dosing.
- o. The end of treatment visit should occur 30 days after the last dose of study treatment (± 7 days) or before starting another line of treatment, whichever comes first.
- p. After patients come off treatment they will be followed up at 3, 6, 9, and 12 months and then every 6 months for 3 years for survival and progression of disease via either clinic visits or phone calls.
- q. Adverse events will be followed from the time of consent until 30 days after treatment discontinuation (100 days for SAE's).
- r. For patients in the expansion phase of the study, mutation testing is required within 1 year of registration (see 3.1.6 for details)

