Please note: This eligibility criteria is also applicable for patients enrolled for the preliminary expansion cohort to conduct preliminary efficacy analysis.

NOTE: Tissue or blood cell free DNA are allowed for genomic profiling of tumor. Profiling should have been performed at a CLIA certified lab ≤1 year prior to registration.

NOTE: Patients in the dose escalation phase are not required to have such mutations. Although genomic profiling is not required for dose escalation patients, it is encouraged in these patients prior to or after study registration if feasible.

3.1.7 Patients must be age ≥ 18 years; both male and females are eligible.

3.1.8 Patients must exhibit an ECOG performance status of ≤2.

3.1.9 Patients must have adequate organ and bone marrow function ≤ 14 days prior to registration, as defined below (Note: Blood transfusion or growth factors is not permitted within 14 days of registration):

absolute neutrophil count	≥ 1.5 x 10 ⁹ /L
hemoglobin	≥ 9 g/dL
platelets	≥ 100 x 10(9)/L
Total bilirubin	≤ 1.5 x ULN
Alanine amino transferase and aspartate aminotransferase	≤ 5 x ULN
Calculated creatinine clearance according to the Cockcroft and Gault equation	≥ 50 mL/min

3.1.10 Females of child-bearing potential (FOCBP) and men who are sexually active with FOCBP must agree to follow instructions for method(s) of contraception for the duration of treatment and the designated post-treatment period (5 months for females and 7 months for males; see Appendix A for details on appropriate contraception methods)

NOTE: A FOCBP is any woman (regardless of sexual orientation, having undergone a tubal ligation, or remaining celibate by choice) who meets the following criteria:

- Has not undergone a hysterectomy or bilateral oophorectomy
- Has had menses at any time in the preceding 12 consecutive months (and therefore has not been naturally postmenopausal for > 12 months)

3.1.11 FOCBP must have a negative pregnancy test ≤ 7 days prior to registration.

3.1.12 Patients must be able to swallow oral medication.

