4.2 Treatment Administration

Table 4.1: Dosing of Nivolumab and Veliparib

Drug	Dose	Route	Schedule
Nivolumab (Opdivo)	C1-4: 240mg C5+: 480mg	IV	Cycle 1-4: every 14 days Cycle 5+: every 28 days until progression of disease, intolerable toxicity, or withdrawal of consent
Veliparib	Phase I: Starting dose 300mg (see 4.3 for escalation) Phase Ib: MTD	PO	Twice a day about 12 hours apart starting 7 days before C1D1 (Induction monotherapy) continuing until progression of disease, intolerable toxicity, or withdrawal of consent

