- In the absence of clear alternative etiology, all events of an inflammatory nature should be considered to be immune-related
- Topical or inhaled steroid therapy should be considered for low-grade events
- Systemic corticosteroids should be considered for a persistent low-grade event or for a severe event
- More potent immunosuppressives (i.e. infliximab, mycophenolate mofetil, etc.) should be considered for events not responding to systemic steroids

If the investigator has any question in regards to an AE being an irAE, the investigator should immediately contact the principal investigator. Treatment modifications will not be required for AEs that are clearly not attributed to investigational drugs (such as an accident) or for laboratory abnormalities that are not deemed to be clinically significant.

Nausea and vomiting have been commonly observed in clinical trials with veliparib. Gastrointestinal toxicities, predominantly nausea and vomiting, were observed with veliparib as single-agent therapy and most frequently reported at higher doses (300 – 400 mg BID). Of the subjects treated with single agent veliparib at 300 – 400 mg BID dose levels, 15% required dose reduction, 5% delayed or interrupted dosing and 2% discontinued due to nausea. To optimize dose intensity and maintain subject quality of life, early initiation or prophylactic management with scheduled anti-emetic therapy (5HT-3 antagonists, metoclopramide, prochlorperazine) and/or lorazepam should be considered. In addition, it has also been observed that tolerance to these toxicities may develop over time. Management should include counseling regarding these toxicities and may include interruption of dosing, dose modification or veliparib discontinuation.

Treatment modifications may be required in the event of treatment-related toxicity. General guidelines regarding treatment modification are provided in Table 4.5 and 4.6. **Dose modifications should be implemented only if toxicities are attributed to respective drugs (nivolumab or veliparib). If there is uncertainty or overlapping toxicities, both drugs should be held and or dose modified according to the guidelines.**

All toxicities will be graded according to NCI CTCAE V4.03 (Appendix B).

Should a female patient become pregnant or suspect she is pregnant while participating in this study, she should inform her treating physician immediately. Similarly if a male patient impregnates a female, the treating physician should be informed.

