APPENDIX A- CONTRACEPTION REQUIREMENTS

Investigators shall counsel FOCBP and male subjects who are sexually active with FOCBP on the importance of pregnancy prevention and the implications of an unexpected pregnancy. Investigators shall advise FOCBP and male subjects who are sexually active with FOCBP on the use of highly effective methods of contraception from the time of treatment initiation to 5 months (for FOCBP) or 7 months (for males with FOCBP partners) after the last dose of nivolumab. Highly effective methods of contraception have a failure rate of < 1% per year when used consistently and correctly.

At a minimum, subjects must agree to the use of two methods of contraception, with one method being highly effective and the other method being either highly effective or less effective as listed below:

HIGHLY EFFECTIVE METHODS OF CONTRACEPTION

- a) Male condoms with spermicide
- b) Hormonal methods of contraception including combined oral contraceptive pills, vaginal ring, injectables, implants, and intrauterine devices (IUDs) such as Mirena® by FOCBP subject or male subject's FOCBP partner. Female partners of male subjects participating in the study may use hormone based contraceptives as one of the acceptable methods of contraception since they will not be receiving study drug.
- c) Nonhormonal IUDs, such as ParaGard®
- d) Tubal ligation
- e) Vasectomy.
- f) Complete Abstinence*

*Complete abstinence is defined as complete avoidance of heterosexual intercourse and is an acceptable form of contraception for all study drugs. Subjects who choose complete abstinence are not required to use a second method of contraception, but female subjects must continue to have pregnancy tests. Acceptable alternate methods of highly effective contraception must be discussed in the event that the subject chooses to forego complete abstinence.

LESS EFFECTIVE METHODS OF CONTRACEPTION

- a) Diaphragm with spermicide
- b) Cervical cap with spermicide
- c) Vaginal sponge
- d) Male Condom without spermicide*
- e) Progestin only pills by FOCBP subject or male subject's FOCBP partner
- f) Female Condom*

*A male and female condom must not be used together

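### No pregnancy test is scheduled before the first veliparib dose; the stated windows allow up to 21 days between the last negative test and that dose

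*Combined protocol and SAP*

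**What the plan says.** **Tests.** Inclusion criterion 3.1.11 reads: "FOCBP must have a negative pregnancy test ≤ 7 days prior to registration". In Table 5 (Section 5.0) the pregnancy-test row is marked at Screening and at Cycle 1 Day 1, and the Induction Day 1 cell is empty. Footnote g gives the same two time points: women of child-bearing potential "must be tested within 7 days prior to registration as well as C1D1 (within 24 hours prior to nivolumab treatment".

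**Start of dosing.** Table 4.1 (Section 4.2) gives the veliparib schedule as "Twice a day about 12 hours apart starting 7 days before C1D1 (Induction monotherapy". Footnote n of Table 5 confirms a 7-day monotherapy induction. Footnote c, which is attached to the Screening and Induction column headings, states: "The maximum time interval between registration and the first dose of study drug will be 14 days".

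**Other pregnancy provisions.**
- 3.1.10: women of child-bearing potential, and men sexually active with them, "must agree to follow instructions for method(s) of contraception for the duration of treatment and the designated post-treatment period".
- Appendix A: contraception runs "from the time of treatment initiation to 5 months (for FOCBP" after the last nivolumab dose.
- Section 4.4: "Should a female patient become pregnant or suspect she is pregnant while participating in this study, she should inform her treating physician immediately".
- 3.2.17 excludes pregnant patients, and 7.2.6 bars further dosing once a patient is pregnant.
- Table 4.5, the veliparib toxicity table, has an entry for embryo-fetal toxicity.

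**The concern.** The only test timed close to dosing is tied to nivolumab, but exposure begins with veliparib a week earlier. By requiring a repeat within 24 hours of nivolumab, footnote g does not rely on the screening result alone at C1D1. The same reasoning applies to the first veliparib dose, yet no comparable test is set there.

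A woman who conceives after the screening test, or whose pregnancy was too early to detect at that point, can start veliparib with the schedule followed exactly. Unless she suspects the pregnancy and reports it, the first scheduled chance to find it is C1D1, after about a week of twice-daily dosing. What is at stake is an avoidable fetal exposure that the protocol's own exclusion and stopping rules are meant to prevent.

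**Working it through.** The plan states no figure for this interval, so there is nothing to reproduce. The limits follow from adding its windows.

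**Inputs**
- Screening test to registration: 0 to 7 days (3.1.11; footnote g).
- Registration to first dose of study drug: 0 to 14 days (footnote c).
- First veliparib dose to C1D1: 7 days (Table 4.1; footnote n).
- C1D1 test: up to 24 hours before nivolumab (footnote g).
- Veliparib: two doses a day (Table 4.1).

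**Last negative test to first veliparib dose**
- Minimum: 0 + 0 = 0 days.
- Maximum: 7 + 14 = 21 days.

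**Last negative test to the C1D1 retest**
- Maximum: 7 + 14 + 7 = 28 days, or 27 if the retest is done a full 24 hours before nivolumab.

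**Veliparib doses taken before the retest**
- 6 × 2 = 12 to 7 × 2 = 14.

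**Sensitivity to the reading of footnote c.** If the first dose of study drug meant nivolumab at C1D1, the maximum gap to veliparib would be 7 + 14 − 7 = 14 days, still with no test before veliparib. Footnote c is attached to the Induction column and veliparib is the first drug given, so 21 days is the supported reading.

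**Does anything else close the gap?**
- Footnote b allows 14 days before registration for laboratory tests in general. The stricter 7 days for the pregnancy test governs, so footnote b neither widens nor narrows the gap.
- 3.1.10 and Appendix A cover the treatment period onward. Neither requires contraception between the screening test and Induction Day 1.
- Appendix A notes that abstinent female subjects are to go on having pregnancy tests. It gives no time point and covers one subgroup.
- Section 4.4 depends on the patient suspecting a pregnancy, so it does not detect an unrecognised one.

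**After the change.** With a test at most 24 hours before the first veliparib dose, the maximum gap falls from 21 days to about 1.

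**The case against.** The case for leaving the schedule alone is that it is coherent and already layered. Footnote g agrees with 3.1.11. Every woman of child-bearing potential has a negative test before registration and a repeat at C1D1, has agreed to contraception, is told to report a suspected pregnancy and stops dosing if pregnant. Contraception is required from Induction Day 1, so the induction week is covered. Twenty-one days needs both windows used to their limits. The remaining risk is a pregnancy conceived before Induction Day 1 and missed at screening, among very few patients.

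Much of this stands. It is a gap in the safety schedule, not a contradiction, and 21 days is a maximum. Three further limits are fair:
- A test at Induction Day 1 would also miss a very recent conception, so it reduces the risk without removing it. The C1D1 repeat remains useful for that reason.
- Table 5 has no pregnancy test after C1D1, although both drugs continue until progression, intolerability or withdrawal of consent. That is a separate gap which this change does not address.
- The documents contain no embryo-fetal data for veliparib. Table 4.5 refers only to a potential hazard to the fetus.

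None of this supplies a test before the first dose. The safeguards listed either begin at treatment initiation or rely on the patient's own suspicion. Small numbers limit how often the gap could matter, not the consequence of a single exposure.

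**Conclusion.** The concern holds. The protocol requires no pregnancy test at or just before the first veliparib dose. Its windows allow 0 to 21 days from the last negative test to that dose, and about 12 to 14 doses before the retest. This rests on reading footnote c as referring to veliparib, which its position in Table 5 supports.

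The people affected are the women of child-bearing potential among the 6 further patients planned, plus any replacements under Section 4.10. The documents do not say how many of the 6 had been enrolled by Amendment 7, so the number still to benefit from that group could be anywhere from 0 to 6. They also give no count of women of child-bearing potential and no probability of pregnancy.

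This is a participant-safety matter with no bearing on any endpoint or analysis. It should be corrected because the gap is preventable and the remedy is small.

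**What to change.** In Table 5, mark the pregnancy test at Induction Day 1 and keep the C1D1 test as a repeat. Amend footnote g to require three things: the existing test within 7 days before registration; a negative serum or urine test within 24 hours before the first dose of any study drug, at Induction Day 1; and the existing repeat within 24 hours before nivolumab at C1D1. Criterion 3.1.11 can stay as it is.

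Secondarily, start the Appendix A contraception requirement no later than the screening pregnancy test, and word 3.1.10 to match.

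The cost is one extra urine or serum test per woman of child-bearing potential. Induction Day 1 already includes a physical exam, chemistry and blood count, and footnote l says: "Study labs will be collected for tumor markers pre-dose on Induction Day 1". No new visit is needed. The text change is a minor amendment, but under Section 11.2 it still needs review and approval by the appropriate local, institutional and governmental bodies and by both drug suppliers.

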2.2 Secondary Objectives & Endpoints

2.2.1 To evaluate the safety and tolerability of nivolumab and veliparib in patients with advanced refractory solid cancers and lymphoma with and without mutations in selected DNA repair genes.

The endpoint will be the number, frequency, and severity of adverse events (as defined by the NCI CTCAE v4.03).

2.2.2 To evaluate the efficacy of treatment with nivolumab and veliparib in this population by objective response rate (ORR, defined as partial response (PR) + complete response (CR)), clinical benefit rate (CBR, defined as stable disease (SD) for ≥ 12 weeks, PR, + CR), and Progression Free Survival (PFS, defined as the time from treatment initiation to documented disease progression) using RECIST criteria v1.1 or Lugano criteria.

For the preliminary efficacy analysis, ORR will be done at the first imaging (8 weeks). Preliminary efficacy will be evaluated by RECISTv 1.1. As exploratory analysis, irRECIST will be used to obtain preliminary efficacy as well. All ORR will use the first imaging time point whether RECIST or irRECIST.

2.2.3 To evaluate efficacy of treatment with nivolumab and veliparib in this population by ORR, CBR, and immune-related PFS (irPFS) using irRECIST criteria.

2.2.4 To evaluate Overall Survival (OS) in this population at 3 years from the start of treatment. OS is defined as the time from treatment initiation until death due to any cause.

2.2.5 To evaluate the proportion of patients alive and progression free at 24 weeks in this population.

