4.7.1 Continuation of Investigational Therapy after Progression

In the event of an initial assessment of PD (based on RECIST Version 1.1), a subject may continue to receive the assigned study treatment as long as none of the criteria listed below are met.

1. Confirmed PD: An initial assessment of PD by RECIST 1.1 or Lugano criteria will be confirmed by a repeat evaluation at the next tumor assessment time point, but no sooner than 4 weeks later (see section 6.1.7 & Appendix C, respectively). If any subsequent tumor assessment shows progression per RECIST v1.1 or Lugano criteria in the overall tumor burden (the sum of diameters of target lesions and new lesions), when compared to the initial PD assessment (the sum of diameters of target lesions and new lesions), then PD is confirmed.
2. Meets any of the other investigational product discontinuation criteria (Section 4.6)
3. Clinical symptoms or signs indicating significant PD, for example the benefit-risk ratio of continuing therapy is no longer justified.
4. Decline in ECOG performance status.
5. Threat to vital organs/critical anatomical sites (e.g., spinal cord compression) requiring urgent alternative medical intervention, and continuation of study therapy would prevent institution of such intervention.

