6.3 Immune-related RECIST (irRECIST)

- 6.3.1 In addition to above, tumor response for both solid tumors and lymphoma will be assessed by the irRECIST for investigational purposes, not assessment of primary objective.³⁷ In RECIST v1.1, the appearance of new lesions indicates PD. However, in irRECIST, new measurable lesions are incorporated in the tumor burden, which is used to determine irPD, immune-related partial response (irPR), and immune-related complete response (irCR). New nonmeasurable lesions preclude irCR. Under RECIST v1.1, there is no confirmation for PD. Under irRECIST, responses and irPDs must be confirmed by consecutive scans at least 4 weeks apart, assuming no clinical deterioration. We will define immune-related clinical benefit rate as immune-related stable disease (irSD), irPR, or irCR.

Table 6: Immune-related Response Evaluation Criteria: Overall Response

Tumor Burden (Baseline and New)	Non-Target Lesions (Baseline and New)	Response
Disappearance of non-nodal lesions. All pathologic lymph nodes <10 mm (short axis)	Disappearance of non-nodal lesions. All pathologic lymph nodes < 10 mm (short axis)	irCR
≥30% decrease from baseline	Any	irPR
≥20% increase from nadir and at least 5 mm	Any	irPD
Neither sufficient decrease to qualify for PR, nor sufficient increase to qualify for PD	Any	irSD
Disappearance of all non-nodal lesions. All pathologic lymph nodes <10 mm	Any other than disappearance of all non-nodal lesions and reduction of pathologic lymph nodes <10 mm	irPR
Not all evaluated	Any	irNE

irCR = immune-related complete response; irPD = immune-related progressive disease; irPR = immune-related partial response; irNE = immune-related not evaluable; irSD = immune-related stable disease;

-Tumor burden is the sum of single diameters (short axis for nodal lesions, longest diameter for other lesions) for the target lesions. In subsequent scans, the diameters of new measurable lesions are added to the tumor burden.

-Best overall response based on 2 consecutive measurements at least 4 weeks apart.

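### A first-imaging irRECIST response rate cannot be a confirmed rate as the protocol requires, and the plan both demands and denies confirmation of RECIST progression without saying which scan dates the PFS event

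*Combined protocol and SAP*

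**What the plan says.** **Response.** Section 6.3.1 states "Under irRECIST, responses and irPDs must be confirmed by consecutive scans at least 4 weeks apart, assuming no clinical deterioration". The note under Table 6 adds "Best overall response based on 2 consecutive measurements at least 4 weeks apart". Section 2.2.2 states "All ORR will use the first imaging time point whether RECIST or irRECIST", with the first imaging put at 8 weeks. The same rule stands in the Study Summary objectives and in sections 1.9, 4.3.3, 6.5.2, 10.1 and 10.2. The Study Summary methodology and section 10.3 use a different rule: the best response reached before progression.

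**Progression.** Footnote j of Table 5 says tumors are measured by RECIST 1.1 or Lugano and continues: "Progressive Disease (PD) must be confirmed by repeat scan within 8 weeks". The RECIST definition of PD in section 6.1.7 has no confirmation step, and section 6.3.1 says "Under RECIST v1.1, there is no confirmation for PD". Section 4.7.1, on treatment after progression, says an initial PD by RECIST 1.1 or Lugano "will be confirmed by a repeat evaluation at the next tumor assessment time point, but no sooner than 4 weeks later".

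**Dating.** Sections 2.2.2, 6.5.2 and 10.3 run PFS from treatment initiation until progression is documented. Sections 2.2.5 and 6.5.5 add the proportion alive without progression at 24 weeks. None of them says whether the first or the confirming scan supplies the date.

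**The concern.** These are stated rules that cannot all be followed. An analyst who applies the two-scan rule at the first imaging must report zero irRECIST responses whatever the treatment does. An analyst who ignores it reports an unconfirmed rate under a definition that calls for confirmation. For progression, two analysts can each cite current protocol text and assign the same patient different PFS dates and opposite 24-week outcomes. CBR depends on the same PD call. If the choice is left open until the data are in hand, it can be made with the results in view.

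**Working it through.** **The plan's own figure.** The only numerical efficacy rule is at least 3 responses in 10, said to put the lower exact 90% bound above 10% (section 10.2). The one-sided 90% Clopper-Pearson lower bound is the 0.10 quantile of Beta(x, n − x + 1). For 2/10 it is 5.45% and for 3/10 it is 11.58%, so the rule reproduces. It uses RECIST v1.1 responses, for which no confirmation is stated, so neither contradiction touches it.

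**Scan calendar.** Inputs: 28-day cycles, a 7-day veliparib induction before C1D1, and scans every 8 weeks from C3D1 with a −7 day window (Table 5, footnotes j and n).

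| Scan | Weeks from C1D1 | Weeks from first veliparib dose |
|---|---|---|
| C3D1 | 7–8 | 8–9 |
| C5D1 | 15–16 | 16–17 |
| C7D1 | 23–24 | 24–25 |

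**irRECIST response at first imaging.** One post-baseline scan exists at C3D1 and two are needed, so 0 confirmed responses are possible. The earliest scheduled confirmation is C5D1. An unscheduled repeat 4 weeks after C3D1 would also fall after the scoring point.

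**Shift in a PFS date.** The repeat is at least 4 weeks later under section 4.7.1 and at most 8 weeks later under footnote j, so the shift is 4 to 8 weeks. With the −7 day window, consecutive scheduled scans lie 7 to 9 weeks apart (8 ± 1). The shift can therefore reach about 9 weeks, which overruns footnote j's own limit.

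**One patient at 24 weeks.** PD first seen at C5D1 (week 16–17 from first veliparib) is a failure under first-scan dating. Dated at C7D1 (week 24–25), the same patient may count as progression free. One such patient moves the rate by 1/10 = 10 points among the 10 mutation patients, 1/12 = 8.3 points among the 12 treated at the MTD (6 + 6), or 1/15 = 6.7 points among all 15 (9 + 6).

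**Illustration for a group.** Assumptions, none from the documents: exponential PFS, S(t) = 0.5^(t/median); every event found by scan; every PD confirmed exactly one scan later.

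- *Case A, scans at weeks 9, 17 and 25.* The third scan falls after week 24. First-scan dating gives S(17); confirming-scan dating gives S(9).
- *Case B, scans at weeks 8, 16 and 24, with week 24 counting.* First-scan dating gives S(24); confirming-scan dating gives S(16). The patient whose status changes is then the one with PD first seen at C7D1.

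| Median (weeks) | A: S(17) → S(9) | B: S(24) → S(16) |
|---|---|---|
| 8 | 23% → 46% | 13% → 25% |
| 12 | 37% → 59% | 25% → 40% |
| 16 | 48% → 68% | 35% → 50% |

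At a 12-week median the gap is 22 points in case A and 15 points in case B.

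**The case against.** **Response.** The first-imaging paragraph is introduced for the preliminary efficacy analysis. Sections 2.2.3 and 6.5.3 list irRECIST ORR as an objective of its own, and section 10.3 extends its analyses to irRECIST using best response before progression. Under that rule a confirmed irRECIST ORR can be computed from C5D1 on. This stands: a reader might infer that irRECIST ORR can never be obtained, and the documents do not support that. What cannot exist is a confirmed rate at the first imaging. The first-imaging wording still covers all ORR, so it collides with section 10.3 as well. A reading of response seen at week 8 and confirmed later would reconcile the two, but it is not written.

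**Progression.** Footnote j is an imaging instruction in a schedule table, and the endpoint sections require no confirmation. Section 4.7.1 governs continued treatment and can coexist with unconfirmed PD for PFS, so it is not a further version of the endpoint. Both points stand. The direct conflict is footnote j against sections 6.1.7 and 6.3.1. It stays open because footnote j is not limited to irRECIST or to treatment decisions, and no dating rule overrides it.

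**Tempting extensions.** A reader might infer that a patient who stops after one PD scan would be censored. No passage says so: section 10.3 is silent on unconfirmed PD, and sections 4.8 and 4.9 continue progression follow-up off treatment. A reader might also infer that a planned RECIST versus irRECIST comparison is spoiled. Sections 2.2.2 and 2.2.3 list two separate evaluations, and no comparison is planned.

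**Impact.** irRECIST is exploratory in the preliminary analysis, and PFS and 24-week status are secondary with no threshold. That limits the weight of the point without removing it.

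**Conclusion.** The point holds in two parts. First, irRECIST ORR at the first imaging cannot be a confirmed rate: read literally it is 0 of 10, and the first-imaging rule also conflicts with the best-response rule in section 10.3. This follows from the schedule and needs no assumption. Second, the plan both requires and denies confirmation of RECIST progression and leaves PFS and 24-week status undated. The 4 to 8 week shift (about 9 with the window) comes from the documents' own numbers.

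The 15 to 22 point change in the 24-week proportion is an illustration only. It rests on the assumed exponential curve, the 12-week median, confirmation of every PD one scan later, and where the third scan falls relative to week 24. No size was worked out for CBR. The 3-of-10 success rule is untouched. The text should be corrected before analysis, but the study's main efficacy decision does not depend on it.

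**What to change.** 1. In section 6.3.1 and wherever the first-imaging rule appears, label first-imaging irRECIST ORR as unconfirmed. Report confirmed best irRECIST ORR separately once the confirming scan is available, and reconcile the first-imaging rule with the best-response rule in section 10.3 and the Study Summary.
2. In sections 6.1.7 and 10.3, state that RECIST/Lugano PFS, CBR and 24-week status count the first scan meeting PD, and that confirmed irPD is dated back to the first irPD scan.
3. Reconcile footnote j of Table 5 with sections 4.7.1, 6.1.7 and 6.3.1. How treatment continuation is decided is for the investigators; no rule is proposed here.

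The cost is wording, with no added scans or patients. Confirmed irRECIST ORR would be reported about 8 weeks later than the first-imaging rate, and RECIST PFS may look slightly shorter than if confirming scans were used.
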